3.6.2. Secondary Data collection

Obstetrical, delivery and neonatal outcome data will be extracted from patient medical charts and will include information on pregnancy complications (e.g., hypertensive disorders of pregnancy, diabetes in pregnancy), delivery (e.g., type and mode of delivery, type of labour, live/stillbirth outcome) and newborn outcomes (e.g., gestational age at birth, birthweight, Apgar scores, NICU admission, need for resuscitation, IV antibiotics and other medications, feeding method from birth to hospital discharge).

Chart reviews will also be conducted if additional information is required to complete/verify the maternal and infant(s) data collection, and/or new information is revealed through participant correspondence. Participants who have an unanticipated delivery at a non-participating hospital site or hospital site without research coordinator support will be asked to sign an 'authorization for release of information' form to allow the research team access to their medical records for data extraction.

3.7. Sample Collection, Shipping and Analysis

3.7.1. Sample collection

Participants will be asked to contribute biological samples. We will allow participants to choose the scope of sample collection at each time-point. Samples will include maternal blood; breastmilk/chestmilk (postpartum collection only); and newborn blood (including cord blood at delivery). (Table 2)

Sampling will be coordinated alongside routine clinical collections where possible to minimize burden to participants. If participating hospital sites have sufficient capacity and resources, participants will be given the option to (1) return to the hospital or affiliated community clinic for sample collection/drop-off; (2) schedule a home visit with a research nurse/coordinator for sample collection/pick-up; (3) mail-in samples, if dried blood spot is preferred by the participant.

For the protection of all parties, both the Site Investigator/Delegate conducting the appointment and the participant will be directed to answer a series of self-assessment questions to assess likelihood or risk of COVID-19 infection before attending in-person visits.

[figure not shown]

Table 2. Sample collection schedule for vaccinated participants

	Visit 1	Post-vaccination Follow-up ³				Delivery
		Visit 2	Visit 3	Visit 4	Visit 5	
Maternal blood ¹	X	X	X	X	X	X
Baby(ies) blood ^{1,2}		X	X	X	X	
Breast/Chest milk ²		X	X	X	X	X
Cord blood						X
Placenta						X

¹Blood samples will be taken as peripheral blood draws, or as dried blood spot samples, as per participant preferences.

²Baby(ies) and milk samples will only be collected after delivery.

³Post-vaccination follow-up schedule will be the same for all vaccine doses (dose 1 or dose 2, if applicable).

- Visit 2 will be scheduled for ≥ 14 days after 1st dose and prior to 2nd dose
- Visit 3 will be scheduled for ≥ 14 days after 2nd dose and prior to visit 4
- Visit 4 will be scheduled for 90 days \pm 14 days after last dose
- Visit 5 will be scheduled for 180 days \pm 14 days after last dose
- If participant is getting a 2-dose vaccine, 1-month follow-up for data collection for dose 1 will occur before dose 2 administration.
- If participant is getting a 2-dose vaccine, and dose 2 scheduling is delayed (for any reason – federal/provincial/local recommendations, participant reasons), data and sample collection will be done approximately every 3 months (~120 days) until dose 2 is administered

Blood samples

To enhance feasibility, maternal and infant blood samples will be collected as either peripheral whole blood or as dried blood spot samples, as per participant preferences.

Peripheral blood will be drawn via venipuncture. Cord blood will be collected immediately after delivery. Serum will be isolated from blood samples. Where possible, serum aliquots will be frozen at $\leq -20^{\circ}\text{C}$ until shipment.

For participants who prefer dried blood spot sampling, blood will be drawn by finger- (maternal), or heel-prick (newborn) using a sterile lancet. Blood drops will be collected on to protein saver cards, dried and stored protected from light in a climate-controlled setting until shipment.

Breastmilk/Chestmilk

To assess the potential for antibody transfer to breastmilk/chestmilk, breastmilk/chestmilk will be collected at the delivery visit, and each subsequent postpartum visit, if the participant chooses to breastfeed/chestfeed their newborn.

Breastmilk/chestmilk will be collected by hand expression or by pump into a sterile container. Where possible, samples will be divided into smaller aliquots. Samples will be frozen at $\leq -20^{\circ}\text{C}$ until shipment.

[figure not shown]
Placental biopsies

Placental biopsies will be taken from the umbilical side of the placenta, evenly spaced around the cord insertion site. Samples will be flash frozen in liquid nitrogen or on dry ice and stored at $\leq -20^{\circ}\text{C}$ until shipment.

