3.7.3. Sample Analysis

Data derived from sample analysis will be linkable to the data file generated from primary and secondary data collection.

Antibody Response to Vaccination

[figure not shown]
Blood and breastmilk/chestmilk samples will be evaluated for antibodies to SARS CoV-2 and neutralizing antibodies to assess maternal and newborn immune responses to maternal vaccination in pregnancy. All samples will be analyzed using a high-throughput enzyme-linked immunosorbent assay based on previously published methods.^{12,13} The assay probes for IgA, IgM and IgG anti-SARS-CoV-2 antibodies and also maintains sensitivity in the detection of antibodies raised against variants of concern: P1, B.1.1.7 and B.1.351. The serological assay detects antibodies against the nucleoprotein (N), the receptor binding domain (RBD) and the full trimeric spike (S). Test sensitivity is 100% at 10 days post-symptoms and specificity is 99.2% as tested against pre-pandemic samples (manuscript in preparation). Such a strategy can distinguish infection-acquired immunity (against N+S+RBD) vs vaccine-induced immunity (S+RBD only). We will also run Neutralization assays (snELISA) on the full spike protein, based on previously published methods.¹⁴ A positive cut-off will be established, equal to the mean of the optical density (OD) values of the negative control samples on the respective plate plus 2x the standard deviation of the OD value distribution from pre-COVID-19 plasma/serum. Background-corrected OD values will be divided by the cut-off to generate signal-to-cutoff (S/CO) ratios. Samples with S/CO values greater than 1.0 will be considered positive. Relative antibody levels measured against a standard curve will also be reported.

Biomarker evaluation

To add understanding to the immunological microenvironment driving the quality and quantity of maternal and newborn antibody responses to maternal COVID-19 vaccination, serum samples will be analyzed for relevant biomarker expression (e.g., serum cytokines). Multiplex immunobead-based assays (BioRad) will be used to quantify serum cytokines.

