- **Stop the Spread Ottawa (SSO) participants:** Non-pregnant females of reproductive age without known history of SARS-CoV-2 infection who received at least one COVID-19 vaccine dose. SSO is an ongoing Ottawa-based, 1000-person prospective cohort study designed to investigate the SARS-CoV-2-specific immune response on COVID-19 convalescent and COVID-19 vaccinated individuals. A total of 126 non-pregnant individuals of reproductive age who have received a COVID-19 vaccine have been enrolled to date. Participants provide monthly blood samples post-vaccination using the same protocols described for the PLAN-V study protocol and are followed for 10 months, allowing for comparison across the PLAN-V time points.

Exposures: The exposure of interest is maternal COVID-19 vaccination in pregnancy (PLAN-V Study) or while not pregnant (SSO Study)

Outcome Measures: The primary immunological outcome measure will be antibody titres acquired from COVID-19 vaccination in pregnant women/individuals will be compared to those of non-pregnant women/individuals. Secondary outcomes will include vaccine reactogenicity, as well as nature and frequency of vaccine-related adverse events.

Sample analysis. Blood serum samples will be evaluated for SARS CoV-2 specific antibodies and neutralizing antibody titres, as well as antibody subclass distributions where appropriate. Samples will be analyzed using the methods described in Section 3.7.3.

Data Sources: Immunogenicity data (including seroconversion rates and antibody titres), vaccine-related data (including product information, reactogenicity and adverse events), and participant characteristics (including sociodemographics, health behaviour risks and medical history) will come from the PLAN-V and the SSO study datasets. The PLAN-V and SSO datasets are both stored at the OHRI, and data elements are aligned thereby facilitating robust comparison of outcome measures.

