4. STATISTICAL ANALYSIS

Descriptive summary statistics will be presented for the study sample, and will include sociodemographic information, obstetrical histories and delivery details. Data will be summarized using frequency distributions for categorical variables, means and medians for continuous variables. A sex and gender-based analysis plus (GBA+) framework will be applied throughout to investigate both sex and gendered related aspects of vaccination among pregnant and their infants including, social and geographic position, race, age, sexuality, sex and gender.

Relative antibody levels will be reported on all positive tests as geometric mean (GM) and their 2-sided 95% confidence intervals (CIs). The maternal response to vaccination will be determined by anti-SARS-CoV-2 antibody levels in maternal serum. Antibody GM with 95% CIs will be compared across time points and between study groups for each sample type. The contribution of IgG subclasses to the total SARS-CoV-2 antibody response will also be reported. Extent and duration of antibody transfer to breastmilk/chestmilk will be evaluated. Infant antibody titres will also be examined to investigate the extent and duration of passive immunity conferred through antibody transfer via the placenta or breastmilk/chestmilk, if any.

Cytokine data will be correlated to detected antibody isotype titres to identify integrated, multi-factorial maternal and newborn immune response signatures to COVID-19 vaccination.

We will account for timing of maternal vaccination in pregnancy/postpartum, vaccine product, number of vaccine doses, COVID-19 infection history, and receipt of other vaccines (mother/child) within the study follow-up period in all analyses.

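### Dried blood spots and venous serum can be mixed by participant preference with no adjustment for collection matrix, and the serum-based comparisons do not say what happens to spot donors

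*Protocol*

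**What the plan says.** **Collection (Protocol Section 3.7.1 and Table 2).** The protocol states that "maternal and infant blood samples will be collected as either peripheral whole blood or as dried blood spot samples", according to participant preference. Table 2 has a single row for maternal blood and a single row for baby blood; the choice between venous draw and dried spot is a footnote to those two rows. Also, "We will allow participants to choose the scope of sample collection at each time-point". For spot donors, "blood will be drawn by finger- (maternal), or heel-prick (newborn) using a sterile lancet" and the drops go onto cards. Cord blood follows the other route: "Cord blood will be collected immediately after delivery. Serum will be isolated from blood samples". No spot option is described for cord blood.

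**Assay (Section 3.7.3).** "All samples will be analyzed using a high-throughput enzyme-linked immunosorbent assay based on previously published methods". The positivity cut-off is the mean optical density of the plate's negative controls plus twice the standard deviation seen in pre-pandemic plasma or serum. No elution, conversion, bridging or separate cut-off for spots is stated.

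**Analysis (Section 4).** Relative antibody levels are reported as geometric means (GMs) of positive tests. "Antibody GM with 95% CIs will be compared across time points and between study groups for each sample type". "The maternal response to vaccination will be determined by anti-SARS-CoV-2 antibody levels in maternal serum". The factors to be accounted for in all analyses are timing of vaccination, product, number of doses, infection history and other vaccines. Collection matrix is not among them.

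**Sub-studies.** Objective 3 (COPE) requires maternal blood and cord blood at delivery, and analyses maternal and cord serum. Objective 4 (SSO) requires maternal blood samples; "Blood serum samples will be evaluated for SARS CoV-2 specific antibodies and neutralizing antibody titres".

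**The concern.** A spot and a venous serum sample from the same person on the same day need not give the same reading. If they do not, a change of matrix between visits looks like a change in antibody level, and a difference in spot use between groups looks like a group effect. Neither can be separated from the real effect unless matrix is recorded and used in the analysis.

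Three outcomes are exposed: persistence of maternal titres, seroconversion defined as a four-fold rise over baseline (Section 5), and persistence of antibody in the infant. The infant series is the most exposed, because it starts from cord serum at delivery and may continue with heel-prick spots. The cut-off adds a second path: it decides which samples are positive, and only positive samples enter the GM, so a cut-off that does not suit spots also changes who is counted.

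Separately, the protocol offers a spot in place of venous blood but determines the maternal response in serum. It does not say whether a spot donor is analysed, pooled or lost.

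**Working it through.** **1. The plan's own figure.** Section 5 claims 93% to 95% power for 95% versus 80% seroconversion with 150 PLAN-V participants. Taking the comparators as 100 COPE dyads (the protocol says more than 100) and 126 SSO participants, two-sided alpha 0.05 and a continuity-corrected normal approximation:

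- 150 v 100: pooled rate 0.890, null SE 0.0404, alternative SE 0.0438, correction 0.0083. z = (0.15 − 0.0083 − 1.96 × 0.0404)/0.0438 = 1.43, power 92.3%.
- 150 v 126: pooled rate 0.882, null SE 0.0391, alternative SE 0.0398, correction 0.0073. z = (0.15 − 0.0073 − 1.96 × 0.0391)/0.0398 = 1.66, power 95.2%.

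Without the correction the powers are 94.7% and 96.7%. The stated range reproduces closely. It does not involve matrix, so it neither supports nor weakens this point.

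**2. What the documents do not give.** Let r be the spot reading divided by the paired serum reading, and d the difference in spot share between two visits or two groups. Neither is stated. All values of r and d below are assumptions.

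**3. Four-fold seroconversion.** With serum at baseline and a spot at follow-up, measured rise = true rise × r, so the true rise needed is 4/r. With the order reversed it is 4 × r.

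| r | serum, then spot | spot, then serum |
|---|---|---|
| 1.0 | 4.0 | 4.0 |
| 0.9 | 4.4 | 3.6 |
| 0.8 | 5.0 | 3.2 |
| 0.7 | 5.7 | 2.8 |

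The effect on the seroconversion rate depends on how many participants have a true rise between 4 and 4/r. The documents do not say.

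**4. GMs across visits.** If spots and serum are pooled, the apparent GM ratio between two visits is the true ratio × r^d.

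| r | d = 0.25 | d = 0.50 |
|---|---|---|
| 1.0 | 1.000 | 1.000 |
| 0.9 | 0.974 | 0.949 |
| 0.8 | 0.946 | 0.894 |
| 0.7 | 0.915 | 0.837 |

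For scale, Section 5 gives 1.19 as a detectable GM ratio (inverse 0.840). Matrix alone reaches it at d = ln(1/1.19)/ln(r): 0.49 for r = 0.7 and 0.78 for r = 0.8. At r = 0.9 it is never reached, since even d = 1 gives 0.90.

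**5. Infant series.** For an infant with cord serum followed by a spot, the apparent fraction of antibody remaining is the true fraction × r. Every infant who gives cord blood and then a spot changes matrix, whatever that family's preference, because no spot route is described for cord blood.

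**6. The sub-studies, side by side.** Eligibility for Objectives 3 and 4 refers to maternal blood. Under the Table 2 footnote that may be a spot, including at delivery. The analysis paragraphs of both sub-studies specify serum, and no serum step is described for spots. A spot donor is therefore eligible but has no sample of the kind to be analysed.

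**The case against.** **The analysis may already separate the matrices.** Section 4 compares GMs by sample type, and that could be read as keeping spots apart from serum. But Table 2 lists the sample types as maternal blood, baby blood, milk, cord blood and placenta, with spot versus venous only as a footnote inside two of them. On that same list, cord and baby blood are separate rows, so the GM comparison need not join them. This has some force. However, the text of Section 3.7.1 counts cord blood as newborn blood, and Section 4 also plans to examine the extent and duration of passive immunity in the infant. Later infant visits can in any case mix venous serum and spots within the baby-blood row.

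**The between-cohort comparisons.** A reader might infer that PLAN-V would be part spots and COPE or SSO all serum, so that a preference for spots would look like an exposure or pregnancy effect. With half of PLAN-V samples as spots at r = 0.7 to 0.8, that would give a spurious GM ratio of 1/0.837 to 1/0.894, or 1.12 to 1.20, close to the 1.19 in Section 5. The documents do not support this reading. Both sub-studies specify serum, and SSO samples are said to follow the same protocols as PLAN-V. Only the conflict over who is eligible and what is analysed remains.

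**Switching between visits is not described.** This is correct. The protocol permits it, because scope is chosen at each time-point and nothing fixes the matrix, but it could also be read as one preference per participant. The step from cord serum to infant spot does not depend on such switching.

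**The effect may be nil.** This stands too. The assay follows published methods, levels are read against a standard curve, and r could be 1.0. A reader might also want a distorted antibody half-life as the measure of harm, but the protocol does not say it will estimate one.

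**A statistical analysis plan could add a matrix term.** It could. But Section 4 already fixes a list of factors for all analyses, and the cut-off and sampling rules are collection and assay decisions that belong in the protocol. Nothing says matrix goes unrecorded; nothing says it is recorded either.

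**Conclusion.** The point stands as possible bias, not demonstrated bias. As written, the plan allows two matrices within one blood sample type, classifies both with a plasma/serum cut-off and omits matrix from the stated adjustment factors. Maternal persistence, four-fold seroconversion and infant persistence may be confounded with matrix if two conditions hold: spots and serum read differently, and spot share differs by visit or group. The maternal part is milder if the reference to maternal serum in Section 4 is applied strictly; spot donors then drop out instead of being pooled. The infant part has no such safeguard.

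The size is unknown. At an assumed ratio of 0.7 to 0.8 the four-fold criterion becomes a true rise of 5.0 to 5.7, and a shift of half in spot share moves a GM ratio by a factor of 0.84 to 0.89. At 1.0 there is no effect.

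For Objectives 3 and 4 the finding is an inconsistency between eligibility and analysis. Its likely consequence is the loss of a subset selected by preference from the 150 behind the power statement.

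**What to change.** - **Section 3.7.1:** state that the matrix of every blood sample is recorded, and encourage one matrix per participant across visits where the participant agrees.
- **Section 4:** state that maternal and between-cohort titre comparisons use serum. Reconcile this with the spot option in Section 3.7.1 and with the maternal-blood eligibility wording of the two sub-studies, saying what happens to spot donors.
- **Section 4, pooled analyses:** wherever spots and serum are combined, notably in infant follow-up, add matrix to the listed adjustment factors and show the serum-only result beside the pooled one.
- **Section 3.7.3:** do not apply the plasma/serum cut-off to spots unless it is shown to hold for them. A small subset with paired serum and spots would show this and would also give the ratio that is now unknown.

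The cost is a few sentences and one data field, plus the paired samples if spots are to be classified. The drawback is a smaller sample in the serum-only analyses, so the number of participants expected to give serum should be set against the 150 in Section 5.

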3.7.2. Sample shipping/return to the Study Coordinating Centre

Samples will be labelled with a unique study ID upon collection. Study ID and corresponding participant information will be retained in site-specific master logs and securely stored on hospital/institutional approved servers. Samples will be shipped to the SCC for processing.

Participants submitting dried blood spot samples will have the option to mail-in these samples. In these cases, participants will be provided with a sample collection kit either in-person at a previous study visit or mailed-out

(sterile swabs, alcohol wipes, lancets, Protein Saver Card labelled with the participant's unique study ID, and detailed instructions) along with a pre-paid return envelope addressed to SCC.

De-identified samples will be distributed to collaborating laboratories for analysis. Unused samples will be retained at the SCC. Sample handling, transportation and packaging will adhere to regulations specified for potentially infectious materials.

3.7.3. Sample Analysis

Data derived from sample analysis will be linkable to the data file generated from primary and secondary data collection.

Antibody Response to Vaccination

[figure not shown]
Blood and breastmilk/chestmilk samples will be evaluated for antibodies to SARS CoV-2 and neutralizing antibodies to assess maternal and newborn immune responses to maternal vaccination in pregnancy. All samples will be analyzed using a high-throughput enzyme-linked immunosorbent assay based on previously published methods.^{12,13} The assay probes for IgA, IgM and IgG anti-SARS-CoV-2 antibodies and also maintains sensitivity in the detection of antibodies raised against variants of concern: P1, B.1.1.7 and B.1.351. The serological assay detects antibodies against the nucleoprotein (N), the receptor binding domain (RBD) and the full trimeric spike (S). Test sensitivity is 100% at 10 days post-symptoms and specificity is 99.2% as tested against pre-pandemic samples (manuscript in preparation). Such a strategy can distinguish infection-acquired immunity (against N+S+RBD) vs vaccine-induced immunity (S+RBD only). We will also run Neutralization assays (snELISA) on the full spike protein, based on previously published methods.¹⁴ A positive cut-off will be established, equal to the mean of the optical density (OD) values of the negative control samples on the respective plate plus 2x the standard deviation of the OD value distribution from pre-COVID-19 plasma/serum. Background-corrected OD values will be divided by the cut-off to generate signal-to-cutoff (S/CO) ratios. Samples with S/CO values greater than 1.0 will be considered positive. Relative antibody levels measured against a standard curve will also be reported.

Biomarker evaluation

To add understanding to the immunological microenvironment driving the quality and quantity of maternal and newborn antibody responses to maternal COVID-19 vaccination, serum samples will be analyzed for relevant biomarker expression (e.g., serum cytokines). Multiplex immunobead-based assays (BioRad) will be used to quantify serum cytokines.

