3.4. Study Outcomes

3.4.1. Primary Outcomes

[figure not shown]
The primary outcome of interest will be immunogenicity of COVID-19 vaccines. We will measure:

- Seroconversion rates in vaccinated mothers
- SARS-CoV-2 antibody titres and their persistence in mothers after vaccination in pregnancy
- Transfer of antibodies to breastmilk/chestmilk
- Transfer and persistence of SARS-CoV-2 antibodies to the neonate/infant over the study period.
- Other immune response markers in mothers and infants
- Comparing infection-acquired and vaccine-acquired immunity against COVID-19 in mothers and newborns (Objective 3: COPE Substudy)
- Comparing immune responses to COVID-19 vaccination in pregnant and non-pregnant women/individuals (Objective 4: SSO Substudy)

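### The only antibody-positivity rule takes its spread from pre-COVID plasma/serum, is not shown to apply to milk, and selects which milk results enter the analysis of a listed primary outcome

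*Protocol*

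**What the plan says.** Section 3.4.1 lists "Transfer of antibodies to breastmilk/chestmilk" among the primary outcomes, and Section 4 adds "Extent and duration of antibody transfer to breastmilk/chestmilk will be evaluated". The Objective 3 (COPE) sub-study also names differences in transfer to milk among its primary outcomes, where samples exist.

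Section 3.7.3 sets the laboratory method:

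- Both fluids are in scope: "Blood and breastmilk/chestmilk samples will be evaluated for antibodies to SARS CoV-2 and neutralizing antibodies".
- They share one assay: "All samples will be analyzed using a high-throughput enzyme-linked immunosorbent assay based on previously published methods".
- The cut-off has a location term, "equal to the mean of the optical density (OD) values of the negative control samples on the respective plate", and a spread term, which is twice the "standard deviation of the OD value distribution from pre-COVID-19 plasma/serum".
- Background-corrected ODs are divided by the cut-off, and "Samples with S/CO values greater than 1.0 will be considered positive".
- Relative levels read from a standard curve are reported as well.

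The rule is not split by sample type. The protocol gives no negative panel, cut-off or specificity for milk. Its specificity of 99.2% refers to pre-pandemic samples whose fluid is not stated.

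Section 4 then ties levels to the call. Geometric means are reported on positive tests, and they are compared over time and between groups for each sample type.

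**The concern.** A cut-off of mean plus 2 SD keeps its intended false-positive rate only if the tested sample comes from the negative distribution that supplied the mean and the SD. For milk, the SD is stated to come from another fluid. If negative milk ODs are more spread out than negative plasma/serum ODs, the rule passes too many negatives. If they are less spread out, the rule is stricter than intended and low true positives are lost. The protocol gives no information on which applies.

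The quantitative results do not avoid the problem. With geometric means restricted to positive tests, a milk sample just under the cut-off is left out of the mean instead of being counted as a low value. At late visits, where levels may have fallen towards the cut-off, its position affects both how many milk samples remain and how low their mean can go. What is at stake is the reported extent and duration of transfer to milk.

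**Working it through.** The protocol states no error rate or power figure that depends on the milk cut-off, so there is no figure to reproduce. The check asks what the stated rule implies for antibody-negative milk.

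**Inputs from Section 3.7.3**

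- Multiplier of the SD: 2.
- Source of the SD: pre-COVID plasma/serum.
- Source of the mean: the plate's negative controls, fluid not stated.

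**Inputs not in the protocol (assumed, shown as a range)**

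- k = SD of negative milk OD divided by SD of negative plasma/serum OD.
- m = (mean of negative milk OD minus plate-control mean) divided by the plasma/serum SD.
- Negative ODs are normal.

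**Formula**

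False-positive rate in negative milk = 1 − Φ((2 − m)/k).

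**Main case: plate controls match milk (m = 0)**

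Only the spread term can then be wrong.

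| k | Cut-off in milk SDs (2/k) | False-positive rate |
|---|---|---|
| 0.75 | 2.67 | 0.4% |
| 1 | 2.00 | 2.3% |
| 1.5 | 1.33 | 9.1% |

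The row k = 1 is what the rule delivers if the plasma/serum SD does apply to milk.

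**Conditional case: shift in the mean (k = 1)**

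This applies only if the plate controls are not milk and background correction does not remove the difference.

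| m | False-positive rate |
|---|---|
| −1 | 0.1% |
| −0.5 | 0.6% |
| +0.5 | 6.7% |
| +1 | 15.9% |

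**Link to the primary outcome**

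Section 3.7.3 calls a sample positive when its ratio exceeds 1.0. Section 4 reports geometric means on positive tests, for each sample type. Followed as written, the set of milk results in the geometric mean is the set that passes a cut-off built partly from plasma/serum. No other passage removes milk from this sequence.

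**The case against.** The strongest reply is that the cut-off is only partly a plasma/serum quantity. Its mean comes from the plate's own negative controls, which could be milk on milk plates, and ODs are background-corrected before the ratio is formed. This stands, and it is why the mean-shift figures are only conditional. It does not reach the SD, which remains a plasma/serum quantity even with matched controls.

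The protocol also gives no milk mean, SD or dilution, so neither the size nor the direction of an error can be derived. This stands too. The normal-theory 2.3% is itself only nominal: the stated specificity of 99.2% would mean 0.8% false positives in whatever fluid was tested.

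The cut-off sentence follows the one on the surrogate neutralization assay, and the assays rest on published methods that may cover milk. However, no other cut-off is given for either assay, and the rule refers to samples without limiting them to serum.

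Some stronger readings are tempting but unsupported:

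- *Milk positivity will be inflated, or the negative distribution is known to be wrong.* The protocol shows neither. It shows only that the distribution used is not demonstrated to fit milk.
- *Duration is read from the visit at which milk turns negative, or percent-positive milk is an endpoint.* Section 4 says only that extent and duration will be evaluated, and no percent-positive milk endpoint is defined.
- *The Objective 3 comparison is biased.* If both groups' milk is assayed under Section 3.7.3, the same cut-off applies to both. That comparison is cross-sectional at delivery, and its sample-analysis paragraph names only maternal and cord serum. No differential bias follows.
- *The cohort's lack of unexposed milk makes a milk cut-off impossible.* The existing reference material is pre-COVID, hence from outside the cohort, and a milk reference could be external too.

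Finally, the positive-only geometric mean can be criticised for blood as well. That is a separate matter. For milk it matters here because it carries an unvalidated call into the primary outcome.

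**Conclusion.** The point holds in a limited form. The protocol applies one positivity rule to all samples, including milk, and its spread term is taken from plasma/serum. Nothing in the document supports using that spread for milk, so the rule does not control the milk false-positive rate. With normal negatives and matched plate controls, the rate is 0.4% to 9.1% for a milk SD of 0.75 to 1.5 times the serum SD, against 2.3% if the two are equal. These ratios are assumptions, and the true size and direction are unknown.

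The practical consequence is certain from the text: the call decides which milk results enter the geometric means that bear on a listed primary outcome. This should be changed because a better analysis uses measurements already planned, not because a particular bias has been shown.

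**What to change.** In Sections 3.7.3 and 4:

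1. State that the signal-to-cutoff call based on the plasma/serum SD does not apply to milk.
2. Report and analyse the standard-curve level for every milk sample, separately for IgA, IgG and IgM, with no positivity filter.
3. State how values below the detection limit are handled.
4. Give a percent-positive for milk only if a cut-off from milk without SARS-CoV-2 exposure is available.

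The cost is wording. Standard-curve levels are already to be reported and the assay already probes the three isotypes, so no new participant samples are needed. The downside is that there is no simple percent-positive for milk unless suitable reference milk can be obtained.
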